#### 6.1.2 Treatment period(s)

Spesolimab will be administered as a single dose i.v. infusion in the clinic.

If deemed necessary by the investigator (i.e. if the flare symptoms persist), a second dose of 900 mg spesolimab may be administered one week after the initial infusion.

IRT transactions are required to obtain all medication kit number assignments. Dates and times of infusions will be recorded in the patient's records and eCRF.

### **6.1.3 Follow up period and trial completion**

Patients will visit the investigator at approximately week 1, week 4 and week 16 after only one single drug administration. If the patient requires a second dose of spesolimab, visits will be re-scheduled based on the date of the last infusion, i.e, patients will visit the investigator at approximately week 1, week 2, week 5, and week 17 after initial dose of spesolimab. Additional visits within the 16-week follow-up period can be planned according to standard clinical practice. Visits may also be conducted by phone or video if judged appropriate by the investigator. At all visits any new or changes in previously reported AEs and concomitant therapies will be recorded in the patient's chart and eCRF.

Patient's participation in the trial will end after conclusion of the 16-week follow-up period after the last infusion / drug administration. The Trial Completion eCRF page will be completed at this time.

A patient will be considered lost to follow-up if the investigator is not able to contact the patient despite multiple attempts. Every effort must be made to contact the patient: at least two telephone contacts plus one mailing should be documented in the patient's chart.

If a patient experiences a new GPP flare (following the resolution of a previous flare with spesolimab treatment) after the 16-week follow-up period, the patient may re-enter in the trial with the same patient number and be treated again with spesolimab, providing eligibility criteria are still met and the overall trial is still running. The same dosing and follow-up requirements apply as for the previous flare.

In the situation that a patient experiences a new GPP flare within the 16-week follow-up period and the physician wishes to treat this new flare with spesolimab, eligibility needs to be re-assessed and agreed upon with the BI clinical team.

Then, in case of re-entry due to a new GPP flare within the 16-wks follow-up period, the patient will end the current follow-up period, and restart the trial from the screening for eligibility. If eligibility criteria is met, and permission from BI is granted (see above), the patient can be treated again to receive a new dose of spesolimab. After infusion, the patient is followed-up for 16-weeks after the latest dose of spesolimab. Also for this scenario, after one week, a second dose of spesolimab can be administered, if deemed necessary by the treating physician.

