## FLOW CHART

Trial Period	Screening		Treatment	Follow-up Period		
	V1 	V2 	V3	V3-2 	V4	V5/ EoS 
Week			1	2	4 / 5 	16 / 17 
Day		1*	8	15	29 / 36 	113 / 120 
Window			±1d	±3d	±7d	±7d
Informed consent	X					
Infection testing 	X					
Demographics	X					
Medical history	X					
Physical examination	X	X 	(X) 	(X) 	(X) 	(X) 
Vital signs	X	X 	(X) 	(X) 	(X) 	(X) 
Pregnancy test 	X 					
Safety laboratory tests (Local lab) 	X	(X) 	(X) 	(X) 	(X) 	(X) 
Review of in-/exclusion criteria	X	X 				
IRT transaction	X	X	X 			
Dispense/administration study drug		X	X 			
Adverse events	X	X 	X	X	X	X
Concomitant therapy	X	X 	X	X	X	X
Study Completion						X

EoS, end of study; IRT, Interactive Response Technology; V, Visit.

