**\*The day of first study drug administration = Day 1. All subsequent study Days are counted from this Day 1.**

- 1: Visit 1 and Visit 2 can be on the same day if required (see also footnote 7).
- 2: Should a patient prematurely discontinue from the treatment, every effort should be made to keep the patient in the trial and complete all of the remaining study visits. If a patient is not willing to follow the whole visit schedule, the EOS Visit (Visit 5) should be conducted at 16 weeks after the last spesolimab administration at a minimum. If patients refuse to return to the study site, early EoS visit should be completed at the timing of prematurely discontinuation and then at least safety information should be collected by phone at 16 weeks after the last spesolimab administration.
- 3: In case of persistent flare symptoms after a single infusion of spesolimab, a second IV dose can be administered at Visit 3 (Day 8). When a second dose is administered at investigator's discretion, IRT call is required at Visit 3 and all procedures/measurements listed for Visit 3 should be performed prior to dosing.
- 4: If patients receive a second i.v. dose of spesolimab at Visit 3 (Day 8), additional visit (Visit 3-2) is required at Day 15 and Visit 4 and Visit 5 (EoS) should be shifted by 1 week, i.e. Visit 4 at Week 5 and Visit 5 at week 17.
- 5: Physical examination, vital signs and safety laboratory test shown with parentheses "(X)" are optional and will be performed according to standard clinical practice and when deemed appropriate by the investigator.
- 6: Infection testing includes tuberculosis, hepatitis B, hepatitis C, and HIV assessments (see [Table 5.2.3:1](#)).
- 7: These procedures do not need to be repeated/performed when V1 and V2 are performed on the same day.
- 8: Only applicable for women of childbearing potential. S – serum pregnancy test.
- 9: Safety laboratory tests at screening visit (Visit 1) include liver function test, haematology test, infection screening test and if a woman of childbearing potential, pregnancy test, and will be performed locally. Please refer to Section [5.2.3](#) for further details.

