#### *Residual Effect Period*

The Residual Effect Period (REP) of spesolimab is 16 weeks. This is the period after the last dose with measurable drug levels and/or pharmacodynamic effects still likely to be present.

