#### 5.2.4.2 Adverse event collection and reporting

##### 5.2.4.2.1 AE Collection

The investigator shall maintain and keep detailed records of all AEs in the patient files. The following must be collected and documented on the appropriate CRF(s) by the investigator:

- From signing the informed consent onwards until the individual patient's end of study (16 weeks after last dose of spesolimab, or at the time of withdrawal of participation): all AEs (serious and non-serious) and all AESIs.
- After the individual patient's end of study: the investigator does not need to actively monitor the patient for new AEs but should only report any occurrence of cancer and trial drug-related SAEs and trial drug-related AESIs of which the investigator may become aware of by any means of communication, e.g. phone call. Those AEs should however not be reported in the CRF.
- Upon patient re-entry into the trial, the patient should be re-evaluated to ensure that eligibility criteria are still met and the overall trial is still running in order to assess AEs (serious and non-serious) and AESIs.

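### The ±7-day window lets the last visit fall 6 to 8 days before the 16-week adverse-event period ends, and no later contact is scheduled

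*Combined protocol and SAP*

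**What the plan says.** The sections on duration agree with one another:

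- The Residual Effect Period paragraph in section 1.2: "The Residual Effect Period (REP) of spesolimab is 16 weeks".
- Sections 3.1 and 6.1.3: a patient's "participation in the trial will end after conclusion of the 16-week follow-up period after the last infusion / drug administration". Section 6.1.3 has the Trial Completion page filled in at that point.
- Section 5.2.4.2.1: all adverse events (AEs) and AEs of special interest (AESIs) are collected until the individual "end of study (16 weeks after last dose of spesolimab, or at the time of withdrawal of participation"). After that, monitoring is passive. Only cancers and drug-related SAEs and AESIs that come to the investigator's attention are reported, and they stay out of the CRF.
- Section 7.1.1: treatment-emergent events are those from start of treatment to the end of the residual effect period (REP), 16 weeks after the last dose.

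The schedule is looser:

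- The Flow Chart puts Visit 5/EoS at Day 113 (one dose) or Day 120 (two doses), with a window of ±7 days, and marks "Study Completion" at that visit only.
- The Flow Chart note on Day 1: "All subsequent study Days are counted from this Day 1". Footnote 4: after a second dose "Visit 4 and Visit 5 (EoS) should be shifted by 1 week".
- Visit 3, where a second dose may be given, is Day 8 ±1 day.
- Section 6.1.3: after a second dose, "visits will be re-scheduled based on the date of the last infusion", yet the same sentence then gives the weeks as counted from the initial dose.

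**The concern.** The visit labelled end of study may be held about a week before the period for which the protocol collects and counts adverse events has run out. Section 5.2.4.2.1 leaves the duty to collect formally open after an early Visit 5, but nothing in the schedule discharges it. A site that reads Visit 5 as end of study will move to the passive rule. Non-serious events, and SAEs or AESIs judged unrelated, in the remaining days would then not reach the data that section 7.1.1 tabulates.

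Occurrence of treatment-emergent AEs is the primary endpoint, and occurrence of SAEs and of AESIs are the secondary endpoints. Efficacy is not assessed. The stake is a slight under-count, and lengths of observation that differ between patients through scheduling alone.

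A minor related gap concerns a patient who starts re-entry screening for a new flare within 16 weeks and is then not re-dosed. Section 6.1.3 ends the current follow-up on re-entry and starts a new one only once an infusion has been given. The general 16-week rule in sections 3.1, 5.2.4.2.1 and 6.1.3 would keep that patient in follow-up. Re-dosed patients, and those never put forward for re-treatment, are not affected.

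**Working it through.** **Inputs.** REP 16 weeks (section 1.2). First dose on Day 1, Visit 5 on Day 113 or 120 ±7 days, Visit 3 on Day 8 ±1 day (Flow Chart and its notes).

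**The plan's own days.** 16 × 7 = 112 days. One dose: 1 + 112 = Day 113. Second dose on Day 8: 8 + 112 = Day 120. Both nominal days are right, so only the minus side of the window is at issue.

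**Shortfall** = (day of last dose + 112) − (nominal Visit 5 day − 7).

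| Last dose | REP ends | Earliest Visit 5 | Days after last dose | Shortfall | Share of 112 days |
|---|---|---|---|---|---|
| Day 1 (single) | Day 113 | Day 106 | 105 | 7 | 6.25% |
| Day 7 (second) | Day 119 | Day 113 | 106 | 6 | 5.4% |
| Day 8 (second) | Day 120 | Day 113 | 105 | 7 | 6.25% |
| Day 9 (second) | Day 121 | Day 113 | 104 | 8 | 7.1% |

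If Visit 5 is instead anchored to the actual last infusion, as part of the sentence in section 6.1.3 suggests, the shortfall is 7 days in every row. No reading removes it.

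**Is another contact fixed at 16 weeks?** Footnote 2 sets a 16-week floor for the EoS visit, but it applies to patients who discontinue treatment prematurely, and only "If a patient is not willing to follow the whole visit schedule". The 16-week phone call is for those among them who refuse to return, with parallel provisions in sections 3.2.4.1 and 5.2.4.2.1 for premature discontinuation. Additional visits under section 6.1.3 are optional. Ordinary completers have no such floor.

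**Effect on an occurrence proportion.** The documents give no usable event rates, so true 16-week occurrences p of 5%, 10% and 20% are assumed, with a constant event rate and nothing collected after Visit 5. With a shortfall of s days:

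seen = 1 − (1 − p)^((112 − s)/112)

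| Case | p = 5% | p = 10% | p = 20% |
|---|---|---|---|
| Every visit 7 days short: seen | 4.69% | 9.41% | 18.88% |
| Loss, points | 0.31 | 0.60 | 1.12 |
| Every visit 8 days short: seen | 4.65% | 9.32% | 18.72% |
| Loss, points | 0.35 | 0.68 | 1.29 |
| Visits spread evenly over −7 to +7 days: seen | 4.92% | 9.84% | 19.70% |
| Loss, points | 0.08 | 0.16 | 0.30 |

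For the last case the mean shortfall is (1 + 2 + … + 7)/15 = 28/15 = 1.87 days, or 1.67% of 112. Visits on or after day 112 count as no shortfall, because section 7.1.1 stops at the end of the REP.

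**The case against.** The best reply is that a visit window does not redefine the collection period. Section 5.2.4.2.1 ties end of study to 16 weeks after the last dose, not to Visit 5. Section 6.1.3 completes the trial record only once the 16 weeks are over. Sections 3.1 and 6.1.3 call the visit weeks approximate, and section 6.1.3 allows extra visits and phone or video contact. On that reading a Day 106 visit does not close the patient, and a reminder to sites would be enough.

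Part of this stands. The obligation does continue, so the analysis rules themselves do not contradict one another. But the Flow Chart labels this visit end of study and marks completion there, no contact is scheduled to meet the remaining obligation, and the optional visits need not happen. The approximate wording loosens the visit, not the collection or counting period.

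The passive reporting after end of study is no remedy either. Apart from cancer it covers only drug-related SAEs and AESIs that become known, and it bypasses the CRF.

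The objection on size is fair. The 6-to-8-day range applies only when Visit 5 is counted from Day 1; anchored to the last infusion the shortfall is 7 days. Few patients are likely to count towards the primary endpoint only through the final week: in the open-label phase I GPP study (1368.11, section 1.2.3) every patient had at least one AE. There is no recruitment goal. At an assumed 30 to 100 patients, the even-spread loss of 0.08 to 0.30 points is about 0.02 to 0.3 of a patient (0.0008 × 30 to 0.0030 × 100).

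The re-entry point is largely answered by the general rule in section 5.2.4.2.1 and would not justify an amendment alone.

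**Conclusion.** The concern holds. Under the Flow Chart, Visit 5 can be held 6 to 8 days before the 16-week period ends (7 days after a single dose, or under anchoring to the last infusion), and completers have no scheduled contact after it.

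The consequence is small: at most 0.3 to 1.3 percentage points on a 5% to 20% occurrence in the worst case, and 0.1 to 0.3 points if visits are spread evenly. Those figures rest on assumed event rates, a constant rate over the 16 weeks, the assumed visit timing, and no collection after Visit 5. Any collection that sites do make afterwards reduces them. How many patients would start re-entry screening and not be re-dosed cannot be derived from the documents.

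The trial is single-arm and descriptive, so no inference changes. The change should still be made: it brings the schedule into line with the period over which every endpoint is counted, and it gives completers the 16-week floor that footnote 2 already gives some discontinuers.

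**What to change.** 1. In the Flow Chart, set the Visit 5 window to 0/+7 days, counted from 16 weeks after the actual last infusion, and use that single anchor in section 6.1.3. The earliest Visit 5 becomes Day 113 after one dose, or Day 119, 120 or 121 after a second dose on Day 7, 8 or 9, and the shortfall is zero. Alternatively, keep ±7 days and require a phone AE contact at or after last dose + 112 days whenever Visit 5 is earlier.
2. Leave the section 7.1.1 cut-off at 16 weeks.
3. In section 6.1.3, reconcile the re-entry paragraph with the general rule by one sentence: AE collection for the earlier dose continues through re-screening and to 16 weeks after that dose, unless a new dose is given.

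The cost is two wording changes in an amendment covering the planned 15 to 20 sites. The first option gives up a little scheduling flexibility at a visit that section 6.1.3 already allows by phone or video. The alternative adds one call for each patient seen early.

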## **7. STATISTICAL METHODS**

Exploratory descriptive statistics of demographic and safety data will be presented.

### **7.1 PLANNED ANALYSES**

Analyses will be based on the treated set (TS) which includes all patients who have been administered spesolimab.

#### **7.1.1 Safety analyses**

In general, safety analyses will be descriptive in nature and will be based on BI standards. No hypothesis testing is planned.

Adverse events will be coded using the Medical Dictionary for Drug Regulatory Activities (MedDRA). Standard BI summary tables and listings will be produced. Statistical analysis and reporting of adverse events will concentrate on treatment-emergent adverse events, i.e. all adverse events occurring between start of treatment and end of the REP, a period of 16 weeks after the last dose of trial medication. Adverse events that start before first drug intake and deteriorate under treatment will also be considered as 'treatment-emergent'. All adverse events with an onset between start of treatment and end of the REP, a period of 16 weeks after the last dose of trial medication, will be assigned to the on-treatment period for evaluation.

All treated patients will be included in the safety analysis.

Frequency, severity, and causal relationship of adverse events will be tabulated by system organ class and preferred term. after coding according to the current version of the Medical Dictionary for Drug Regulatory Activities (MedDRA) at database lock.

## **8. INFORMED CONSENT, TRIAL RECORDS, DATA PROTECTION, PUBLICATION POLICY, AND ADMINISTRATIVE STRUCTURE**

The trial will be carried out in compliance with the protocol, the ethical principles laid down in the Declaration of Helsinki, in accordance with the ICH Harmonized Guideline for Good Clinical Practice (GCP), relevant BI Standard Operating Procedures (SOPs), the Japanese GCP regulations (Ministry of Health and Welfare Ordinance No. 28, March 27, 1997) and other relevant regulations. Investigators and site staff must adhere to these principles. Deviation from the protocol, the principles of ICH GCP or applicable regulations as will be treated as “protocol deviation”.

In addition, the trial also will be carried out in compliance with Good Post-Marketing Study Practice (GPSP) upon commencement of the post marketing clinical trial.

Standard medical care (prophylactic, diagnostic and therapeutic procedures) remains the responsibility of the investigator.

The investigator will inform the sponsor or delegate immediately of any urgent safety measures taken to protect the trial patients against any immediate hazard, as well as of any serious breaches of the protocol or of ICH GCP.

The Boehringer Ingelheim transparency and publication policy can be found on the following web page: [trials.boehringer-ingelheim.com](https://trials.boehringer-ingelheim.com). The rights of the investigator and of the sponsor with regards to publication of the results of this trial are described in the investigator contract. As a rule, no trial results should be published prior to finalization of the Clinical Trial Report.

The certificate of insurance cover is made available to the investigator and the patients and is stored in the ISF.

### **8.1 TRIAL APPROVAL, PATIENT INFORMATION, INFORMED CONSENT**

This trial will be initiated only after all required legal documentation has been reviewed and approved by the respective IRB and CA according to national and international regulations. The same applies for the implementation of changes introduced by amendments. Prior to patient participation in the trial, written informed consent must be obtained from each patient (or the patient’s legally accepted representative) according to ICH-GCP and to the regulatory and legal requirements of the participating country. Each signature must be personally dated by each signatory and the informed consent and any additional patient-information form retained by the investigator as part of the trial records. A signed copy of the informed consent and any additional patient information must be given to each patient or the patient’s legally accepted representative.

The investigator or delegate must give a full explanation to patients in the trial based on the patient information form. A language understandable to the patient should be chosen, technical terms and expressions avoided, if possible. The patient must be given sufficient

time to consider participation in the trial. The investigator or delegate obtains written consent of the patient's own free will with the informed consent form after confirming that the patient understands the contents. The investigator or [REDACTED] delegate must sign (or place a seal on) and date the informed consent form. If a trial collaborator has given a supplementary explanation, the trial collaborator also signs (or places a seal on) and dates the informed consent.

Re-consenting may become necessary when new relevant information becomes available and should be conducted according to the sponsor's instructions. The consent and re-consenting process should be properly documented in the source documentation.

## **8.2 DATA QUALITY ASSURANCE**

A risk-based approach is used for trial quality management. It is initiated by the assessment of critical data and processes for trial subject protection and reliability of the results as well as identification and assessment of associated risks. An Integrated Quality and Risk Management Plan or alternative plan, in line with the guidance provided by ICH Q9 and ICH-GCP E6, for fully outsourced trials, documents the rationale and strategies for risk management during trial conduct including monitoring approaches, vendor management and other processes focusing on areas of greatest risk.

Continuous risk review and assessment may lead to adjustments in trial conduct, trial design or monitoring approaches. A quality assurance audit/inspection of this trial may be conducted by the sponsor, sponsor's designees, or by IRB / IEC or by regulatory authorities. The quality assurance auditor will have access to all medical records, the investigator's trial-related files and correspondence, and the informed consent documentation of this clinical trial.

## **8.3 RECORDS**

CRFs for individual patients will be provided by the sponsor. For drug accountability, refer to section [4.1.5](#).

### **8.3.1 Source documents**

In accordance with regulatory requirements, the investigator should prepare and maintain adequate and accurate source documents and trial records that include all observations and other data pertinent to the investigation on each trial patient. Source data as well as reported data should follow the "ALCOA principles" and be **attributable, legible, contemporaneous, original and accurate**. Changes to the data should be traceable (audit trail). Data reported on the CRF must be consistent with the source data or the discrepancies must be explained.

The current medical history of the patient may not be sufficient to confirm eligibility for the trial and the investigator may need to request previous medical histories and evidence of any diagnostic tests. In this case, the investigator must make at least one documented attempt to retrieve previous medical records. If this fails, a verbal history from the patient, documented in their medical records, would be acceptable.

If the patient is not compliant with the protocol, any corrective action e.g. re-training must be documented in the patient file.

For the CRF, data must be derived from source documents, for example:

- Patient identification: gender, year of birth (in accordance with local laws and regulations).
- Patient participation in the trial (substance, trial number, patient number, date patient was informed).
- Dates of patient's visits, including dispensing of trial medication.
- Medical history (including trial indication and concomitant diseases, if applicable).
- Medication history.
- Adverse events and outcome events (onset date (mandatory), and end date (if available)).
- Serious adverse events (onset date (mandatory), and end date (if available)).
- Concomitant therapy (start date, changes).
- Originals or copies of laboratory results and other imaging or testing results, with proper documented medical evaluation (in validated electronic format, if available).
- Completion of patient's participation in the trial (end date; in case of premature discontinuation document the reason for it).
- Prior to allocation of a patient to a treatment into a clinical trial, there must be documented evidence in the source data (e.g. medical records) that the trial participant meets all inclusion criteria and does not meet any exclusion criteria. The absence of records (either medical records, verbal documented feedback of the patient or testing conducted specific for a protocol) to support inclusion/exclusion criteria does not make the patient eligible for the clinical trial.

